6.2. Key Definitions

6.2.1. Baseline Value

Unless otherwise specified, the baseline value for any variable will be the last value taken prior to the start of medication. This includes screening assessment. Unscheduled measurements prior to first administration date will be considered in the calculation of baseline values.

6.2.2. Change from Baseline and Percent Change from Baseline at a Post-Treatment Time Point

Change from baseline is defined as the difference between the post-treatment value and the baseline value.

Percent change from baseline is defined as $100^* (\text{change from baseline}) / \text{score at baseline}$.

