8.1. Primary Efficacy Endpoint and Analysis

The primary efficacy endpoint is the change from baseline in Schirmer test I (without anesthesia) versus Week 4. The primary analysis is based on the FAS population. Missing data will be replaced by means of the Last Observation Carried Forward (LOCF) method.

The Schirmer test I will be summarized using descriptive statistics for continuous variables by treatment and visit. The change from baseline value will also be summarized for all post-baseline visits. The same summary analysis will be provided after pooling the treated patients (20 µg/mL BID arm and 20 µg/mL TID) together. Comparison (descriptive in nature) of the change from baseline of each treatment versus placebo will be performed by means of a t-test at each timepoint.

The primary analysis will be performed by means of an analysis of variance including only treatment as main factor followed by pre-planned comparisons from Vehicle and rhNGF dosages according to Williams' procedure.

The first comparison will compare the rhNGF TID dose to the Placebo using Williams test.

In case of significant result then the rhNGF BID dose will be compared to the Placebo; if the result is not significant then the test will be stopped.

Description of the Williams' Test:

μ_0 = Effect of Placebo

μ_1 = Effect of rhNGF BID

μ_2 = Effect of rhNGF TID

Hypotheses:

$H_0: \mu_0 = \mu_1 = \mu_2$

$H_1: \mu_0 <= \mu_1 \leq \mu_2$

The test develops into two phases:

* First step

Starting from the observed means X_i , determine the maximum likelihood estimates M_i (corrected mean of group i after amalgamation) under the alternative hypothesis.

If X_i satisfies the inequalities written in H_1 then $M_i = X_i$

Otherwise pool any adjacent violators into the same value:

$M_i = (n_i * X_i + n_{i+1} * X_{i+1}) / (n_i + n_{i+1})$ where n_i = sample size of group i.

The process is repeated until the means are completely ordered.

This document is confidential.

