*** Second step**

Calculate the test statistic given by
 $T_k = (M_k - X_0) / s * \sqrt{1/n_0 + 1/n_k}$

where s = root mean square error and X_0 is the observed mean in the placebo group.

The fact that the k th dose level is the minimum effective dose is concluded if $T_j > t_{j,\alpha}$ for all $j \geq k$ where the $t_{j,\alpha}$ values are the critical values reported by Williams [2].

The Schirmer test I values will be also listed.

An explorative sensitivity analysis of the primary endpoint will be conducted including in the analysis of variance the absence/presence of diagnosis of Primary Sjögren's Syndrome and its interaction with treatments as covariates. If the interaction term is statistically significant (at the 0.10 level given its explorative nature), the treatment effects within patients with and without Primary Sjögren's Syndrome will be provided.

For patients already enrolled in the study, the assignment to a strata will be based on Medical history form.

If "Primary Sjogren" is recorded in the Medical condition of the Medical history form then the patient will be assigned to "Presence of Primary Sjogren"; if only "Sjogren" is recorded then the patient will be assigned to "Absence of Primary Sjogren". In all other cases, the patient will be assigned to "Absence of Primary Sjogren".

In order to assess the robustness of results of primary analysis, the Schirmer test I will be also evaluated by means of non parametric Fisher's exact test after applying the following categorization at week 4:

- A patient is defined as "Responder" if the Schirmer test I value at week 4 is greater than 10 mm/5 minutes;
- A patient is defined as "Non responder" if the Schirmer test I value at week 4 is lower or equal than 10 mm/5 minutes.

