8.2.1. Change from baseline in Symptoms questionnaire (SANDE) scores for severity and frequency

The SANDE questionnaire is comprised of 2 questions at each visit:

- (1) How often do your eyes feel dry and/or irritated?
- (2) How severe do you feel your symptoms of dryness and/or irritation are?

One measure frequency of symptoms ranges from "0 mm = rarely" to "100 mm = all of the time," and the other measure severity of symptoms ranges from "0 mm = very mild" to "100 mm = very severe".

The global SANDE score will be calculated by multiplying the frequency score by the severity score and obtaining the square root [4].

Change from baseline at Week 4 will be analyzed using analysis of variance including treatment as factor followed by pre-planned comparisons from Vehicle and rhNGF dosages according to Williams' procedure.

Descriptive statistics (actual and change from baseline) of SANDE scores will be presented by treatment and visit. Comparison (descriptive in nature) of the change from baseline of each treatment versus placebo will be performed by means of a t-test at each timepoint.

This document is confidential.

Symptoms questionnaire (SANDE) scores will be also listed.

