8.2.2. Change from Baseline in Schirmer Test II (with Anesthesia)

The Schirmer test II (with anesthesia) will be summarized using descriptive statistics for continuous variables by treatment and visit. The change from baseline value will also be summarized for all post-baseline visits. Comparison (descriptive in nature) of the change from baseline of each treatment versus placebo will be performed by means of a t-test at each timepoint.

The Change from baseline in Schirmer test II at Week 4 will be analyzed in a similar manner as the Change from baseline to Week 4 in Schirmer test I.

The Schirmer test II values will be also listed.

8.2.3. Change from Baseline in Corneal and Conjunctiva Vital Staining with Fluorescein (NEI Scales)

Corneal staining total score is defined as the sum of scores from 5 corneal areas: Central, Superior, Temporal, Nasal, and Inferior. The score for each area ranges from 0 to 3. Thus, the corneal staining total score can range from 0 to 15.

The conjunctiva is divided into a superior paralimbal area, an inferior paralimbal area and a peripheral area with a grading scale of 0–3 and with a maximal score of 9 for the nasal and temporal conjunctiva.

Thus, the conjunctival staining total score can range from 0 to 18.

Corneal and conjunctiva vital staining total score is the sum of corneal staining total score and conjunctiva total score.

Descriptive statistics (actual and change from baseline) for Corneal and conjunctiva vital staining total score, corneal score and conjunctiva score will be presented by treatment and visit. Comparison (descriptive in nature) of the change from baseline of each treatment versus placebo will be performed by means of a t-test at each timepoint.

The Change from baseline in Corneal and conjunctiva vital staining total score (NEI scales) at Week 4 will be analyzed in a similar manner as the Change from baseline to Week 4 in Schirmer test I.

The Corneal and conjunctiva vital staining score with fluorescein will be listed.

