APPENDIX I SAMPLE SAS CODE IN STATISTICAL ANALYSIS

1) Sample Code for Efficacy Analysis : Schirmer test I

An Analysis of variance will be used for Schirmer test I, followed by Williams test. An example of the SAS code to perform this analysis is below.

```
*****
* SAS Code: GLM (Analysis of variance) followed by William test
* Variables in the model:
*&var=CHG = Change from baseline in Schirmer test I at week 4
*&trt=trt01p = treatment planned
*****,
%macro WILLIAMS(dat = , trt = , var = );
/*##### WILLIAMS TEST #####*/
/*For Williams Test, We Assume a Monotonic Dose Relationship (i.e. x0 <= x1 <= x2 <=... x7 etc.). If this does not occur, then a dose that does not conform (when sorted by dose level) should be combined with next closest dose and averaged. Keep doing this until we get conformance. Note that this relies on comparing vs x0, so x0 should always be lowest result*/
%global lsm1 maxdose contmean;
/*Assign a New Dose Number (Consecutive) for Processing*/
proc sort data = &dat. out = DOSEN (keep = &trt.) nodupkey;
  by &trt.;
run;
data DOSEN;
  set DOSEN;
  DOSEN = _N_;
run;
data &dat.2;
  merge &dat. DOSEN;
  by &trt.;
run;
```

This document is confidential.

```
proc glm data = &dat.2 noprint outstat=STAT_(keep = _TYPE_ DF SS where=(_TYPE_="ERROR"));
  class DOSEN;
  model &var. = DOSEN;
  lsmeans DOSEN / pdiff cl;
  output out = STAT p=LSMEAN r=resid LCL=LCI UCL=UCI STDP=STDERR;
run;

proc sort data = STAT out = STAT2 (keep = &trt. DOSEN LSMEAN LCI UCI STDERR) nodupkey;
  by DOSEN;
run;

/*Get Max Dose Level for Processing*/
proc sql noprint;
  select compress(put(max(DOSEN),best.)) into :MAXDOSE
  from STAT2;
quit;
%put &maxdose.;

/*Get LSMEAN for Placebo/Control for Processing*/
proc sql noprint;
  select compress(put(LSMEAN,best.)) into :CONTMEAN
  from STAT2(where=(DOSEN=1));
quit;
%put &contmean.;

/*Get Number of Observations and Merge Back on to GLM Output*/
proc univariate data = STAT noprint;
  by DOSEN;
  var RESID;
  output out = N N=N;
run;

data STAT_2 (drop = _TYPE_ SS);
  set STAT_;
  if nmiss(DF,SS) = 0 then MSE = SS/DF;
  do DOSEN = 1 to &maxdose.;
    output;
  end;
run;

data STAT2;
  merge STAT2(in=a) N STAT_2;
  by DOSEN;
  if a;
run;

/*Get Dose Level 1 LSMean for Checking Whether Each Dose >= Dose1*/
proc sql noprint;
  select compress(put(LSMEAN,best.)) into :LSM1
```

This document is confidential.

```
from STAT2(where=(DOSEN=1));
quit;
%put &lsm1.;

/*Output All LSMEANS and N for All Dose Levels Present*/

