%macro VAR(var = );
proc sort data = STAT2;
  by MSE DF;
run;
proc transpose data = STAT2 out = STAT2_&var.(drop = _NAME_) prefix=&var.;
  by MSE DF;
  id DOSEN;
  var &var.;
run;
%mend VAR;
%VAR(var = LSMEAN); %VAR(var = N);

data STAT3(drop = _LABEL_);
  merge STAT2_LSMEAN STAT2_N;
run;

data STAT4;
  set STAT3;
  array LSMEAN(&maxdose.); array N(&maxdose.); array DIFF(&maxdose.); array
DENOM(&maxdose.);
  array T(&maxdose.);
  CONTROL = LSMEAN(1);
  do j = 1 to &maxdose.-1;
    if LSMEAN(j) > LSMEAN(j+1) then do;
      EN = N(j+1);
      EMEAN = LSMEAN(j+1);
      NMEAN = N(j+1)*LSMEAN(j+1);
      do k = j to 1 by -1;
        if EMEAN < LSMEAN(k) then do;
          EN = EN + N(k);
          NMEAN = NMEAN + N(k)*LSMEAN(k);
          *EMEAN = (EMEAN*N(k)/(EN)) + ((N(k)*LSMEAN(k))/(EN));
          EMEAN = NMEAN/EN;
          do r = k to j+1;
            LSMEAN(r) = EMEAN;
          end;
        end;
      end;
    end;
  end;
  do j = 2 to &maxdose.;
    DIFF(j) = (LSMEAN(j)-CONTROL);
    DENOM(j) = ((MSE*((1/N(j))+(1/N(1))))**0.5);
    T(j) = DIFF(j)/DENOM(j);
  end;
run;
```

This document is confidential.

```
data STAT5 (drop = EMEAN EN MSE DF j k r DIFF: DENOM:);
  set STAT4;
  array LSMEAN(&maxdose.); array T(&maxdose.); array p(&maxdose.);
  do i = 2 to &maxdose.;
    p(i) = 1 - probmc("Williams",T(i),,DF,i-1);
  end;
run;

%macro OUT(var2=, dat = , out = );
data &out.(keep = DOSE.);
  set &dat.;
  %do i = 1 %to &maxdose.;
    rename &var2.&i.=DOSE&i.;
  %end;
run;
%mend OUT;

%OUT(var2 = LSMEAN, dat = STAT3, out = LSMEAN1);
%OUT(var2 = LSMEAN, dat = STAT5, out = LSMEAN2);
%OUT(var2 = N, dat = STAT5, out = N);
%OUT(var2 = T, dat = STAT5, out = T);
%OUT(var2 = P, dat = STAT5, out = P);

data WILLIAMS (keep = TYPE DOSE1-DOSE&maxdose.);
  retain TYPE DOSE1-DOSE&maxdose.;
  length TYPE $50.;
  set LSMEAN1(in=a) LSMEAN2(in=b) N(in=c) T(in=d) P(in=e);
  if a then TYPE = "LSMeans (Original)";
  if b then TYPE = "MLE";
  if c then TYPE = "No. Obs";
  if d then TYPE = "Williams T Statistic";
  if e then TYPE = "P-Value";
run;
%mend WILLIAMS;
```

This document is confidential.

2) Sample Code for Efficacy Analysis : Schirmer test I in case of presence of many missing data

For RMM, if SAS mixed model is used, the sample SAS codes will be like the following:

```
PROC MIXED DATA=SCHIRMERI;
CLASS usubjid TRT01P visit;
MODEL chg = TRT01P TRT01P * visit /ddfm=kr;
repeated visit / sub = usubjid type = un;
lsmeans TRT01P / cl diff at time = Week4;
```

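### The Williams test is defined only for increases over vehicle, but it is also planned for SANDE and NEI staining, where benefit is a decrease, and no passage reverses the direction

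*SAP*

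**What the plan says.** SAP 8.1 describes one Williams procedure, for Schirmer I. Its alternative orders the means as vehicle ≤ BID ≤ TID. For observed means that break that order, the rule is "Otherwise pool any adjacent violators into the same value". The statistic is the pooled dose mean minus the observed vehicle mean, divided by its standard error. The conclusion is one-directional: "The fact that the k th dose level is the minimum effective dose is concluded if" the statistic exceeds the upper critical value for that dose and every higher one. TID is tested first, and testing stops if it fails.

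The Appendix I macro does the same. It pools whenever a mean is lower than the one before it, subtracts the vehicle mean, and takes the p-value as one minus the Williams distribution function. Its header comment adds: "Note that this relies on comparing vs x0, so x0 should always be lowest result".

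SAP 8.2.1 applies this procedure by name to SANDE: "Change from baseline at Week 4 will be analyzed using analysis of variance including treatment as factor followed by pre-planned comparisons". For staining, SAP 8.2.3 says: "The Change from baseline in Corneal and conjunctiva vital staining total score (NEI scales) at Week 4 will be analyzed in a similar manner" as Schirmer I. SAP 8.3.4 and 8.3.5 repeat the primary analysis for both scales at Week 2, where testing is descriptive only.

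SAP 6.2.2 fixes the sign: "Change from baseline is defined as the difference between the post-treatment value and the baseline value". SANDE runs from 0 mm (rare, very mild) to 100 mm (constant, very severe). The NEI total is a sum of staining grades, 0 to 15 for cornea plus 0 to 18 for conjunctiva, so 0 to 33. No passage gives a reversed alternative, a lower-tail rule or a sign change for either scale.

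**The concern.** For Schirmer I, Schirmer II and TFBUT a higher value is better, so an upward test is right. On SANDE and NEI a patient who improves has a negative change. If rhNGF works, vehicle has the least negative, and so the highest, mean. That is the reverse of the macro's stated precondition.

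The planned test would then miss a real benefit and reward a real worsening. The SANDE Week 4 Williams tables (14.2.2.1.1 for the FAS, 14.2.2.1.2 for the per-protocol set) are marked topline; the NEI ones are not. Two outcomes are plausible: a topline p-value that contradicts the tables beside it, or a direction changed after treatment codes are known.

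**Working it through.** **The plan's own figure.** SAP 3.4 gives one-sided 0.025, about 90% power, difference 5.3 and SD 10.78. Then n = 2 × (10.78/5.3)² × (1.96 + 1.2816)² = 86.94, so 87 per group, as stated. With 76 per group the same approximation gives power 0.858, matching the stated minimum of 85%. The standardised effect is 5.3/10.78 = 0.492. It is used below only as a benchmark.

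**Why the test cannot see a benefit.** Write X0, X1, X2 for the observed vehicle, BID and TID means. With equal groups, the pooled TID mean is the largest of X2, (X1+X2)/2 and (X0+X1+X2)/3. If X0 is the highest of the three, none of these exceeds X0, so the TID statistic is zero or negative and cannot pass an upper critical value. Because TID is tested first, BID is then never tested.

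**Worked example** (illustrative SANDE changes, SD 25, 76 per arm). The standard error is 25 × √(2/76) = 4.06. The critical values are about 2.03 for TID and 1.97 for BID.

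- Benefit, as written: vehicle −10, BID −20, TID −25. All three means pool to −55/3 = −18.33, and T = (−18.33 + 10)/4.06 = −2.06 (−2.055 unrounded) for both doses. Not significant.
- The same data with the sign reversed: T = 10/4.06 = 2.47 for BID and 15/4.06 = 3.70 for TID. Both significant.
- Worsening, as written: vehicle −25, BID −20, TID −10. T = 15/4.06 = 3.70 for TID, which is declared effective.

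**Rejection rates.** Inputs: 76 per arm (SAP 3.4), one-sided 0.025, normal data, and a Williams critical value of 2.027 for two doses on 225 degrees of freedom (numerical integration, supported by simulation). There were 2,000,000 simulated trials per scenario. The table shows how often TID is declared different from vehicle when both doses have the same effect.

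| Effect (SD) | Benefit, as written | Benefit, sign reversed | Worsening, as written |
|---|---|---|---|
| 0.2 | 0.06% | 26% | 26% |
| 0.3 | 0.01% | 51% | 51% |
| 0.4 | 0% | 76% | 76% |
| 0.492 | 0% | 91% | 91% |

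Over three dose patterns (equal effects, BID half of TID, TID only), the ranges are 0% to 0.16% for benefit as written, 22% to 91% for benefit with the sign reversed, and 22% to 91% for worsening declared an effect. The median p-value under benefit runs from 0.79 to above 0.99. These p-values come from the simulated null distribution; the SAS function itself was not run.

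**In scale units** (differences from vehicle and SDs assumed, since the documents give none):

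- SANDE −10 mm (BID) and −12 mm (TID), SD 15 to 35: 0% as written, 99.9% down to 59% reversed.
- NEI −1 point on both doses, SD 2 to 5: 0% to 0.06% as written, 92% down to 26% reversed.

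**What the other displays would show.** For equal effects of 0.2 to 0.492 SD, a two-sided 0.05 t-test of TID against vehicle with pooled error finds the benefit in 23% to 86% of the same trials.

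**The case against.** The strongest reply is that a sensible programmer would orient the test. The Appendix I code is labelled as a sample for Schirmer I. It already needs interpretation: it numbers doses in the sort order of the treatment variable, so the labels must place vehicle first, and the statistic in 8.1 lacks a pair of parentheses. SAP 8.1 calls the means effects, and the staining text asks only for a similar analysis. The macro comment itself warns that vehicle must be lowest.

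The consequence is also softened elsewhere. Topline SANDE summaries by treatment and visit (14.2.2.1.5 and 14.2.2.1.8), descriptive t-tests and 95% CI figures would show the true direction. The macro output lists the original means beside the p-value. SAP 8.2.5 tests worsening of 50% or more separately, and a stratum-by-treatment model is planned for both scales. No alpha hierarchy rests on SANDE or NEI, and no alpha is stated for secondary endpoints.

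Much of this stands as mitigation, and a real worsening would be hard to mistake for benefit in the full report. It does not supply the missing direction. The ordering of vehicle is settled by 8.1, which makes placebo the zero dose; nothing settles the sign. For SANDE the procedure is named outright, and at Week 2 both scales get the primary analysis itself. The t-tests are labelled descriptive, so they do not replace the planned test. It is also true that a one-sided test facing the wrong way has near-zero power by construction; the simulation only sizes what is lost.

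**Conclusion.** The concern holds. Read literally, the Williams tests for SANDE and NEI run in the wrong direction: benefit on TID would be detected in at most 0.16% of trials over the scenarios in SD units, against 22% to 91% with the sign reversed. These rates assume 76 per arm, one-sided 0.025 (stated only for the primary variable's sample size), normal data and effects of 0.2 to 0.492 SD. The sizes depend on those assumptions; the direction does not.

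The scope is two secondary endpoints at Week 4, one of them topline, and their descriptive Week 2 repeats. The primary endpoint, Schirmer II and TFBUT are correct as they stand. IDEEL and the EQ-5D VAS (mixed models) and PGIC (Wilcoxon) do not use this test. This should be corrected, but it does not threaten the primary conclusion.

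**What to change.** In SAP 8.2.1, 8.2.3, 8.3.4 and 8.3.5, state that for SANDE and NEI the Williams procedure is run on an improvement variable, baseline minus post-baseline, derived in the dataset and passed to the macro by name (for example var = IMPR). A minus sign in the macro call will not work, because the argument becomes the response in "model &var. = DOSEN". Equivalently, state the alternative vehicle ≥ BID ≥ TID, with downward pooling and a lower-tail p-value. Keep the present direction for Schirmer I, Schirmer II and TFBUT.

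The cost is one derived variable and one sentence in each of four subsections, made before database lock and unmasking. No new data are needed and the primary analysis does not change.

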8.2.2. Change from Baseline in Schirmer Test II (with Anesthesia)

The Schirmer test II (with anesthesia) will be summarized using descriptive statistics for continuous variables by treatment and visit. The change from baseline value will also be summarized for all post-baseline visits. Comparison (descriptive in nature) of the change from baseline of each treatment versus placebo will be performed by means of a t-test at each timepoint.

The Change from baseline in Schirmer test II at Week 4 will be analyzed in a similar manner as the Change from baseline to Week 4 in Schirmer test I.

The Schirmer test II values will be also listed.

8.2.3. Change from Baseline in Corneal and Conjunctiva Vital Staining with Fluorescein (NEI Scales)

Corneal staining total score is defined as the sum of scores from 5 corneal areas: Central, Superior, Temporal, Nasal, and Inferior. The score for each area ranges from 0 to 3. Thus, the corneal staining total score can range from 0 to 15.

The conjunctiva is divided into a superior paralimbal area, an inferior paralimbal area and a peripheral area with a grading scale of 0–3 and with a maximal score of 9 for the nasal and temporal conjunctiva.

Thus, the conjunctival staining total score can range from 0 to 18.

Corneal and conjunctiva vital staining total score is the sum of corneal staining total score and conjunctiva total score.

Descriptive statistics (actual and change from baseline) for Corneal and conjunctiva vital staining total score, corneal score and conjunctiva score will be presented by treatment and visit. Comparison (descriptive in nature) of the change from baseline of each treatment versus placebo will be performed by means of a t-test at each timepoint.

The Change from baseline in Corneal and conjunctiva vital staining total score (NEI scales) at Week 4 will be analyzed in a similar manner as the Change from baseline to Week 4 in Schirmer test I.

The Corneal and conjunctiva vital staining score with fluorescein will be listed.

8.2.4. Change from Baseline in Tear film break-up time (TFBUT)

Descriptive statistics (actual and change from baseline) for TFBUT will be presented by treatment and visit. Comparison (descriptive in nature) of the change from baseline of each treatment versus placebo will be performed by means of a t-test at each timepoint.

Change from baseline in TFBUT at Week 4 will be analyzed in a similar manner as the Change from baseline to Week 4 in Schirmer test I.

TFBUT values will be listed.

8.2.5. Number of Patients who Experienced a Worsening in Symptom Scores (SANDE) and/or NEI Score $\geq 50\%$ Assessed at Week 4

Number and percentage of patients who experienced a worsening in symptom scores (SANDE) and/or NEI score $\geq 50\%$ assessed at Week 4 will be summarized by treatment group.

Difference, between treatment group (Each active dose – Placebo), in the percentage of patients who experienced a worsening will be tested using a chi-square test.

This document is confidential.

